8. INTERVENTION DISCONTINUATION

MABT sessions will be discontinued for any of the following reasons, but participant will not be withdrawn from study:

1. Participants are inebriated or high from alcohol or drugs such that they are not able to engage in the intervention on more than one scheduled session.
2. If, in consultation with the participant's healthcare providers, there is concern for his/her safety and well-being (e.g., escalation of symptoms).

The participant could be withdrawn from study if, in consultation with the participant's health care providers, there is sufficient concern for his/her safety and well-being that the

participant may be withdrawn and re-directed to more appropriate care. This is described to the participant in the consent process.

9. STATISTICAL CONSIDERATIONS

9.1 General Design Issues

Statistical Hypotheses:

This project has one primary objective with a primary and a secondary hypothesis, and three secondary objectives with a single hypothesis as specified below.

Design Overview: A two-group (n = 165/165), randomized, repeated measures design will be employed. Three hundred thirty individuals with OUD engaged in MAT treatment will be recruited at one of three outpatient treatment sites, Harborview Medical Center, Country Doctor Community Health Centers, and North Olympic Healthcare Network. Enrolled patients will be individually randomized within sites to receive MABT+TAU (experimental group), or TAU only (control). An additional six sessions of MABT will be offered to those randomized to MABT who have continued substance use at six months. Assessments will be administered at baseline, post-intervention (3 months), and at 6, 9, and 12 month follow-up.

Primary Objective: Primary hypothesis: MABT+TAU will result in significantly fewer days of OU compared to TAU only from baseline to 12 months.

The primary outcome is patient-reported days of illicit opioid use. Self-reported substance use is the recommended approach for intervention studies.^[97] Days of illicit opioid use is defined as the number of days in which use of opioids other than MAT (buprenorphine or methadone) are reported. The TLFB method^[3, 4] was determined for alcohol, amphetamines, cannabis, cocaine, hallucinogens, opiates, sedative-hypnotics, and any psychoactive substance for time periods of 0-30 days, 0-90 days, and 0-365 days, the correlations for all substances and for the three time periods ranged from .73 to .95, demonstrating test-retest reliability and validity.^[98]

Primary Objective: Secondary hypothesis: MABT+TAU will result in significantly fewer days of non-opioid substance use compared to TAU only from baseline to baseline to 12 months.

Days of other illicit substance use is defined as the number of days of non-opioid substance use (.e.g. cocaine, methamphetamine, hallucinogens, non-prescribed benzodiazepines). We will also be reporting the number days the participant reports heavy drinking (>=5 drinks/day for males, and >=4 drinks per day for females).

Secondary Objective 1 Hypothesis: MABT+ TAU will result in significantly improved mental health (depression, anxiety, trauma), emotion regulation, interoceptive awareness and mindfulness skills), and physical health distress and pain (symptoms, pain severity, pain interference) compared to TAU only from baseline to 6 months (R33) and baseline to 12 months (R01).

Measures of mental health (distress symptoms and emotion regulation) will include three well-validated scales for diagnostic screening: the 9-item PHQ-9 to screen for depression[6, 7], the 7-item ($\alpha = .92$) GAD-7 for anxiety[8], and the Posttraumatic Stress Disorder Checklist for DSM-5 (PCL-5),[9] which assesses symptoms of post-traumatic stress on a Likert-type scale with 20 items ($\alpha = .94$). The 4th measure, the Difficulty in Emotion Regulation Scale short form (DERS-SF)[10, 99] assesses difficulties in the modulation of emotional arousal. There are 18 items on a Likert-type scale (DERS $\alpha = .93$; DERS short form α ranges from .78 to .91 with original DERS subscales) and four subscales that assess the degree of awareness, understanding, and acceptance of emotions, and the ability to act in desired ways regardless of the emotional state. The 5th & 6th measures, the Freiberg Mindfulness Questionnaire (FMQ) with 14 items[14], and the Multidimensional Assessment of Interoceptive Awareness (MAIA)[15] with 32 items on a Likert-type scale.

Physical symptoms will be assessed using the Medical Symptoms Checklist (MSC) and pain severity and interference using the Brief Pain Inventory (BPI). The MSC measures the frequency (0-8 scale) and severity (0-10 scale) of 29 common physical symptoms.[19] The BPI is a validated, widely used measurement tool for assessing clinical pain. In the U.S. it has been validated in non-cancer patients with pain[18] and HIV-infected patients.[100] The assessment includes 11 questions which provide information on pain severity and pain interference in the past week. Participants are initially asked if they have experienced any significant pain in the past week, and if they respond positively they answer subsequent questions about duration of pain, pain severity and interference. Pain severity is rated from 0 (“no pain”) to 10 (“worst pain imaginable”), and participants are asked to rate their current pain as well as pain at its worst, at its best, and on average in the past week. Pain interference includes information on the impact of pain on general activity, walking, work, mood, enjoyment of life, relations with others, and sleep, asking the participant to rate interference on a scale from 0 (“does not interfere”) to 10 (“completely interferes”), and is reported as the mean of seven questions. Participants who responded that they had no pain in the past week will be coded “0” for pain severity and interference. The BPI will be supplemented with a single question on duration of currently reported pain in order to establish whether the pain is acute or chronic.

Secondary Objective 2 Hypothesis: MABT + MAT will result in significantly reduced opioid craving, and significantly longer retention (days receiving medications), compared to TAU only from baseline to 6 months (R33) and baseline to 12 months (R01).

Opioid craving will be assessed using a single item numeric scale.[5] Participants are asked: “On a scale of 0-10, please indicate how much craving you have experienced during the past week,” with responses anchored at “0=no craving at all” and “10-strongest craving ever”. Retention will be defined as days retained in the program, or time to program discharge. Program discharges are documented in the electronic medical record (EMR) and date of discharge will be extracted from the record.

Secondary Objective 3 Hypothesis: Among participants in both groups who are using substances at 6 months, those in MABT group who receive additional MABT sessions (between 6-9 months) will show improved substance use at 12 months compared to those in TAU.

Exploration of the effectiveness of additional MABT dose offered at 6 months to those with continued substance use compared to those with continued substance use at 6 months in the TAU will be assessed using the Time-Line Follow-Back Interview (TLFB)[3, 4] self-reported as described in in the primary objective.

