5. STUDY INTERVENTIONS

5.1 Interventions, Administration, and Duration

The intervention in this study is Mindful Awareness in Body-oriented Therapy (MABT), administered one-on-one by therapists trained in the MABT protocol at the outpatient treatment site where the participant was recruited from and receives their MAT care. Individuals in the MABT intervention group will receive 8 weekly 1.25 hour one-on-one sessions of MABT between baseline and the 3 month follow-up assessment. There are no restrictions to supportive care, medications, or other treatments which intervention group participants may use during their participation in the study with the exception of additional manual (e.g., massage) and/or mind-body therapies of meditation and yoga during the first three months of study engagement (this information is part of the screening process for enrollment, and will be reiterated by the research coordinator at the time of study enrollment). There are no anticipated adverse effects of the intervention other than the possibility of short-term emotional discomfort.

At six months, those in the MABT treatment group with continued substance use will be offered an additional six sessions of MABT between the 6 month and 9 month assessments.

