5.2 Handling of Study Interventions

Mindful Awareness in Body-oriented Therapy (MABT): The MABT intervention has a well-developed protocol and training manual for research. Used in multiple clinical trials,[83, 85, 86, 93-95] the protocol has an incremental approach for teaching interoceptive awareness skills and developing weekly individualized homework based on session content to promote integration of practice into daily life. Individuals in the MABT treatment group will receive 8 weekly 1.25 hour one-on-one sessions of MABT. Research therapists will be hired and trained to provide the MABT intervention. MABT has three distinct stages (see Table 2). Stage 1 (sessions 1-2), develops body literacy, the ability to identify and articulate sensory awareness. Body literacy training is done in the context of massage therapy to facilitate sensory awareness related to attention to the quality of soft tissue (e.g., muscular tension). Stage 2 (sessions 3-4) focus on interoceptive awareness training to develop the ability to access inner body awareness and begin to make links between physical and emotional sensations. Stage 3 (sessions 5-8) focuses on the development and practice of mindful body awareness involving sustained interoceptive attention which facilitates positive shifts in sensory experience as well as insights that motivate behavior change. Each session begins with a semi-structured check-in to build trust and familiarity between therapist and participant, and ends with session review to facilitate cognitive integration of the session

material and to collaboratively develop the homework for the interim week. The interoceptive training components (stages 1-3) are designed with an incremental approach to facilitate learning, particularly important for individuals with SUD who often have difficulties attending to sensory (physical and emotional) awareness. Individualized homework is based on session content and crafted to promote integration of practice into daily life.

The additional six MABT sessions that will be offered to eligible participants at 6 months will be delivered as explained above and will include all stages of the intervention as outlined in Table 2 but will be individualized to address the intervention components needing the most review (if the participant did not complete MABT initially) or will follow the intervention protocol for delivery of the first 6 of 8 sessions if the received no prior MABT sessions when initially assigned.

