6.2.4 Follow-up Visits

Treatment

Initial Treatment Visit 1 (W1)

- Adverse Events
- MABT Process Evaluation (self-report by interventionists)

Initial Treatment Visit 2-8 (W2 - 11)

- Adverse Events
- MABT Process Evaluation (self-report by interventionists)
- MABT Practice Log (self-reported home practice by participants for use by interventionists)

Additional MABT Sessions 1-6 (W25 - W38)

- Adverse Events
- MABT Process Evaluation (self-report by interventionists)
- MABT Practice Log (self-reported home practice by participants for use by interventionists)

Assessments

Followup1-4 Assessment Visits (W12, W24, W39)

The follow-up assessments will be scheduled 12 weeks, 24 weeks, and 39 weeks from baseline, and takes approximately 45 minutes to complete. Coordinators will make every effort to schedule the assessment near to the target date, but are allowed -2 weeks/+4 weeks to capture follow-up assessment data. In addition to this assessment, we will also gather treatment retention data through electronic medical record (EMR) at the 6 and 12 month assessments.

Should a participant be unable to provide data during the scheduled assessment (e.g., unable to provide a urine sample, or unable to complete the assessment in one sitting), research coordinators have up to 14 days to complete the data collection for the assessment.

W24: The Time-Line Follow-Back Interview (TLFB)[3, 4] results collected at 6 months will be used to determine those in the MABT study group with continued substance use who will be offered six additional MABT sessions between month 6 and 9. Criteria for eligibility for additional MABT sessions is 1) randomized to the MABT + TAU study group, and b) self-report of substance use on the TLFB, including any days of heavy alcohol drinking and excluding marijuana use.

Primary outcome:

- Time-Line Follow-Back Interview (TLFB)[3, 4] will be used to assess self-reported opioid use, and use of other illicit drugs, marijuana, and alcohol.

Secondary outcomes:

- The PHQ-9 will be used to measure depression symptoms.[6, 7].
- The GAD-7 will be used to measure anxiety symptoms.[8]
- Posttraumatic Stress Disorder Checklist for DSM-5 (PCL-5),[9] assesses symptoms of post-traumatic stress on a Likert-type scale.
- Difficulty in Emotion Regulation Scale - short form (DERS- SF)[10] assesses difficulties in the modulation of emotional arousal.

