Secondary Outcomes For comparison of treatment arms on measures of secondary outcomes, we will have 80% power to detect a minimum difference of 0.4 SD. For comparison of medication-assisted treatment retention rates, we hypothesize that retention rates at 12 months will be 60% in the TAU arm and 77% in the MABT arm. The comparison of proportions will have power of 80% to detect this difference. Exploratory Aim: at 6 months after 20% attrition, we expect the total sample to be N = 264 (132 per group) and assume the ability to detect, at minimum, a 15% difference between MABT and TAU groups in proportion of abstinent days. Under these assumptions, the power at 12 months to detect a group difference comparing those using substances at 6 months (nonresponders) in control to those using substances (nonresponders) at 6 months in MABT groups (who have been offered additional sessions) is .65 for a 40% non-responder rate (n = 53 per group). While underpowered, this exploratory aim would provide a reasonable sample size to estimate power for future related research questions and allows us to look at the question of MABT dose and re-engagement for those needing additional treatment support within the primary analysis.

Missing Data: We will evaluate differences in baseline characteristics between participants lost to follow-up versus those who are not. Missing data patterns will also be evaluated including the frequency and percentage of those missing for each variable and the distribution of the number of variables missing. In addition, data collected to the point of lost to follow-up will be compared to the data of those who complete the study to examine possible missing data mechanisms, e.g., missing completely at random (MCAR), missing at random (MAR), or not missing at random (NMAR). Sensitivity analyses will be performed to assess the possible impact of the missing data on the study results. We will consider various methods for missing TLFB including multiple imputation and pattern mixture models.[105] Similar methods will be used for other drug use and opioid craving. We anticipate there should be no missing data for retention since patients who are lost to follow-up are discharged from the program, therefore “missingness” is part of the variable definition.

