9.6 Data Analyses

Primary Analysis To test the primary hypotheses, generalized linear regression models for dependent data will be used to compare percent days abstinent from opioid use in the two study groups between baseline to 6 months for the R33 study aims, and baseline to 12 months for the R01 study aims. Sensitivity analyses will also explore modeling opioid use as percent days abstinent during the assessment periods using Generalized Estimating Equations (GEE) [106] with a logit link and an exchangeable correlation structure. We will fit difference within group correlations structures (unstructured, independent, exchangeable, autoregressive) seeking the correlation structure that combines the fewest parameters with the best measure of fit using Akaike information criterion (AIC) and Bayesian information criterion (BIC). The logarithm of the total number of days in the assessment period will be included as an offset variable to account for the time at risk of relapse. The same analysis will be done to examine percent days abstinent on other illicit drugs and alcohol.

Secondary Analyses Analyses of secondary outcomes (mental and physical health outcomes and opioid craving) will utilize GEE as described above. Longitudinal analyses will examine treatment by time interactions on each of the outcomes. Analyses of retention in medication-assisted treatment will be done using a test of proportions retained in MAT as well as the log-rank test to compare survival curves. A sensitivity analysis will use Cox regression to adjust for pre-treatment covariates. Last, we plan to include exploratory analyses to also examine treatment by gender interactions.

Exploratory Analysis Linear regression model using GEE will be used to explore the effect of additional MABT dose on days abstinent from opioid use and related health outcomes at 12 months among the MABT 6 month non-responders compared to control non-responders. Characteristics of responders will be compared to those of non-responders using t-tests, chi-square, or Fisher's exact tests.

In addition, we will explore the relationship with dose, within the MABT group. Dose response functions will be estimated thorough a regression approach treating the number of sessions as the continuous treatment variable. Such models are appropriate when the treatment intensity is endogenous (that is, selection into treatment depends on both observable and unobservable factors).

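### Objective 3 labels the 12-month difference between MABT and TAU six-month users an effect of the additional sessions, but the comparison also carries the first course and selection at six months

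*Combined protocol and SAP*

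**What the plan says.** Sections 1.2 and 9.1 state the hypothesis for participants still using at the 6-month assessment: "those in MABT group who receive additional MABT sessions (between 6-9 months) will show improved substance use at 12 months", relative to TAU. Section 9.6 plans a GEE regression "to explore the effect of additional MABT dose on days abstinent from opioid use and related health outcomes at 12 months". The groups it sets against each other are the non-responders of the two arms, and it names no adjustment for this contrast.

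On assignment, section 5.1 says that the MABT group "will receive 8 weekly 1.25 hour one-on-one sessions of MABT between baseline and the 3 month follow-up assessment". Under section 6.2.4 the extra six sessions go to those who are "randomized to the MABT + TAU study group, and b) self-report of substance use on the TLFB"; heavy drinking counts as use and marijuana does not. No TAU participant is eligible. Section 5.2 adds that MABT participants who attended nothing at first "will follow the intervention protocol for delivery of the first 6 of 8 sessions", so for them the additional sessions are a first exposure.

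On expectations, section 9.2 assumes that the prior trial's effect (88.6 versus 80.0 percent abstinent days at 12 months) will be similar at 6 months, and section 2.2 reports arm differences at both 6 and 12 months in that trial. For the exploratory aim, section 9.2 says that the 12-month power "is .65 for a 40% non-responder rate (n = 53 per group". It calls the aim underpowered but hopes that it will inform power for later research. It mentions neither carry-over nor selection.

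**The concern.** The two groups of 6-month users differ in three respects:

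1. Only the MABT group was assigned the first eight sessions.
2. Each group is formed by an outcome measured after randomisation. If MABT reduces use by month 6, as the plan expects, those still using in that arm are a more resistant remainder than those still using under TAU.
3. Only the MABT group is offered the step-up.

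The hypothesis and the analysis credit the result to the third alone. Carry-over could make inert extra sessions look useful, and selection could make them look harmful. The hypothesis also refers to participants who receive the sessions, whereas the objective and section 9.2 speak of sessions offered. Restricting to recipients would add self-selection in one arm only. At stake are a causal statement about dose that the design cannot support, and its reuse in planning later studies.

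**Working it through.** **1. The plan's own figure.** 330 × 0.80 = 264, or 132 per arm; 132 × 0.40 = 52.8, rounded to 53. Section 9.2 gives a 15-point difference but no base rate. I assume 0.80 versus 0.95, taking 0.80 from the prior trial's TAU arm, and two-sided alpha .05 as stated for the primary aim. With p̄ the mean of the two proportions,

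power = Φ{ [|p₂ − p₁| − 1.96·√(2p̄(1 − p̄)/n)] / √([p₁(1 − p₁) + p₂(1 − p₂)]/n) }.

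Here p̄ = 0.875, so (0.15 − 1.96 × 0.0642)/0.0626 = 0.385 and power = .65. The stated figure reproduces under that base rate (0.75 versus 0.90 would give .529). The arithmetic is not the problem.

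**2. Carry-over alone, same formula.** Let the extra sessions do nothing and let an 8.6-point first-course effect (0.80 versus 0.886) persist among the 53 per group: (0.086 − 1.96 × 0.0707)/0.0702 = −0.748, a probability of .227. The contrast would then show a significant MABT advantage about 23% of the time, against a nominal .025 in that direction. A persisting effect of 5 points gives .099. The amount of carry-over is an assumption.

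**3. Carry-over and selection together.** Illustrative simulation, 400,000 per arm, extra-session effect zero. All inputs are assumed:
- logit of daily use across people N(−4, SD 3) or N(−5.5, SD 4), within-person SD 1, 90-day binomial counts;
- non-responder means any use in the 6-month window;
- first-course effect of 1.0 to 1.5 logits at 6 months.

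MABT minus TAU, in percentage points of abstinent days at 12 months:

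| First-course effect left at 12 months | Planned contrast, 6-month users | 12-month minus 6-month arm contrast, all randomised |
|---|---|---|
| All | about +4 to +7 | 0 |
| Half | about −0.6 to +1.2 | −1.7 to −3.0 |
| None | about −4 to −8 | −3.7 to −7.0 |

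In the last row, the planned contrast is roughly −4 to −5 at 1.0 logit and −7 to −8 at 1.5 logits. Simulated non-responder rates were 46–62% under TAU and 33–51% under MABT.

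**4. Adjustment, with the first-course effect fully faded.** Adjusting for baseline use only leaves −0.8 to −1.3 points. Adding 6-month use leaves −4.4 to −6.4, because 6-month use is itself changed by the first course. Baseline adjustment deals with selection only. Where the first-course effect persists, it leaves the carry-over and also takes away the selection that was partly offsetting it.

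**5. A second parametrisation.** With an assumed SD of 0.31 for the proportion of abstinent days and no effect of either set of sessions at 12 months, non-responder rates of 45% TAU versus 35% MABT gave −1.2 to −2.4 points, and 48% versus 32% gave −1.9 to −3.8. Adding 8.6 points of carry-over at 45% versus 35% gave +6.2 to +7.4. Selection is smaller here, but the net sign again depends on what is assumed.

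**The case against.** The strongest reply is that the aim is exploratory, is openly underpowered, and supports no confirmatory conclusion. Section 5.2 discloses first exposure among non-attenders, section 5.4 records attendance, and section 9.6 plans a separate within-MABT dose regression that recognises treatment intensity as endogenous. Section 9.2 speaks only of informing power for later questions and does not commit to sizing a dose trial. All of this is fair and lowers the stakes. It does not meet the point: low power is conceded but confounding is not, a larger sample would not remove it, and the within-MABT regression does not supply the missing comparison group.

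The size is also open to challenge. The simulation uses one substance for both selection and outcome, whereas section 6.2.4 selects on any qualifying substance and section 9.6 analyses opioid abstinence first. Simulated TAU abstinence was 86.5–89%, against 80.0 in the prior trial. With half the effect persisting, the biases nearly cancel. This stands: the figures show possible direction and order of size, not the bias to expect in this trial.

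A reader might infer that the common 40% rate invalidates the power figure. It does not. Rates of 46% and 34% would give about 61 and 45 people, and 2 × 61 × 45/106 ≈ 52 as the effective number per group, against 53.

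A reader might also infer that the 12-minus-6-month arm contrast in all randomised participants solves the problem. It keeps the randomised groups, but the table shows zero only under full persistence, and it averages in responders who are never offered the step-up.

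**Conclusion.** The concern holds as a matter of identification and labelling. The planned comparison of 6-month users cannot isolate the extra sessions, because no MABT user is assigned to go without them and no TAU user is offered them. That follows from the design and needs no simulation. With no true effect of the extra sessions, the illustrative contrast runs from about +4 to +7 points through roughly zero to about −4 to −8 points, depending on how much of the first course's effect survives. The planned contrast cannot tell these cases apart.

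The documents do not support reading this as a bias of known direction, or as one of about the prior trial's 8.6 points: the largest values come from the extreme cases, and the inputs are assumed. Nor do they support inferring that the extra sessions are ineffective, or that the primary 12-month comparison of all enrolled participants is compromised.

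**What to change.** - In 1.2, 9.1 and 9.6, restate the target as the initial MABT course plus offered step-up versus TAU among 6-month users, and remove the wording that calls it the effect of the additional dose. Bring the similar wording in 9.3 into line.
- Define the MABT group by the offer of the sessions, not their receipt.
- Adjust the main estimate for baseline TLFB use. Do not adjust it for 6-month use.
- Report non-responder counts by arm and by initial sessions attended (0, 1–5, 6–8).
- State that carry-over remains, that the groups compared are formed after randomisation, and that the extra sessions' own effect is not identified. Do not carry the estimate forward as a dose effect when planning later trials.
- The 12-minus-6-month arm contrast in all randomised participants may be reported to describe how the treatment effect changes, but not as a replacement estimate.

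The cost is revised wording, one covariate and one table, all from data already collected. Who is offered sessions and what is measured do not change. The price is a more modest claim for an exploratory aim.
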